We will contract with NORC at the University of Chicago to recruit 1,230 young adults (aged 18-29) from a combination of their AmeriSpeak panel (approximately N=1000) and a third-party opt-in panel (remainder). NORC will recruit participants, program the survey, administer the survey to eligible participants, and provide the Wake Forest team with a final dataset, where participants are weighted to create a nationally representative sample. Participants who complete the survey will receive a small incentive, as agreed up by their panel, generally worth a few dollars. Participants will complete demographics and tobacco use measures and then will be randomized to one of three conditions. One-third (about 410 participants) will be randomized to the pictorial warning intervention group, 410 to the text-only warning intervention group, and 410 to the no-warning control group. The two intervention groups will see six respective warnings on sample packaging, one at a time. The control group will see the sample packaging once, without a warning. Intervention group participants will respond to measures designed to assess their warning reactions (emotional and cognitive reactions, perceived message effectiveness), and appeal of each package. Control group participants will complete items on package appeal. After viewing all warnings, participants will complete items on behavioral intentions, perceived risks of waterpipe smoking, and knowledge of risks. After completing the study, participants will be provided with a link to the CDC fact sheet about waterpipe smoking and the tobacco quit line number.

Setting

Participants will complete the survey on a computer, tablet, or phone at a location of their choosing.

Subject Selection Criteria

We will conduct an online national probability-based survey with a sample of 1,230 US young adults (18-29 years old) using the AmeriSpeak panel at NORC and a third-party non-probability sample, weighted with the AmeriSpeak sample to be nationally representative.

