There are three goals for the analysis. First, compare WTS intentions between those exposed to text versus pictorial waterpipe warnings. We hypothesize that those exposed to pictorial warnings will have lower WTS intentions than those exposed to text warnings. To test the differences in warnings format on WTS intentions, we will fit a linear regression model using PROC MIXED in SAS to account for the sampling design features (e.g., sample weights, repeated measures). We will then examine experimental condition as a fixed effect with and without adjustment for potential confounders (e.g. sex, race/ethnicity, age, SES, WTS, use of other tobacco products). All tests will be two-sided. For a sample of 400 participants per condition, we will have 80% power to detect differences between the text only and pictorial conditions in waterpipe intentions of 0.24 or greater (corresponding to an effect size 0.16) in a design with 6 repeated measurements having a compound symmetry covariance structure when the standard deviation is 1.5, based on Lipkus & Mays (2018). For comparisons between the text or pictorial warnings and the control condition (which does not have repeated measures), we will have 80% power to detect differences of 0.27 or greater, corresponding to an effect size of 0.18. For all comparison, the correlation between repeated observations on the same subject is 0.6 and the alpha level is 0.05. As a sensitivity analysis, we will perform a subgroup analysis restricted to those reporting that they have not participated in a tobacco study in the past year to examine whether prior participation influences our findings. Second, we will assess the impact of warnings on behavioral antecedents, such as negative affect, cognitive elaboration, perceived risks, and knowledge using separate models, similar to those described above for WTS intentions. Third, we will select four coordinating warnings from each condition (same text in both), with the highest PME scores for use in Aim 3. We will assess the rank order of warnings based on PME scores for the sample as a whole and for subgroups, based on sex, race/ethnicity, sexual orientation, and WTS behavior to determine whether the rankings remain consistent. Ultimately, we will select four text and four pictorial warnings (that match) and are consistently ranked high on PME across subgroups.

Human Subjects Protection

Subject Recruitment Methods

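### The stated detectable differences (0.24 and 0.27 at 80% power) make no allowance for weighting, although the primary model is to use sample weights; the size of the shortfall depends on a design effect the plan does not give.

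*Combined protocol and SAP*

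**What the plan says.** The Analytical Plan (Combined protocol and SAP) fits the primary model for intentions "to account for the sampling design features (e.g., sample weights, repeated measures". The Design section describes about 1,000 members of a probability panel plus opt-in respondents to reach 1,230, with a final dataset "where participants are weighted to create a nationally representative sample". Subject Selection Criteria repeats that the two sources are weighted together.

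The power statement, in the same paragraph of the Analytical Plan, begins: "For a sample of 400 participants per condition, we will have 80% power to detect differences between the text only and pictorial conditions". It gives that text-versus-pictorial difference as one "in waterpipe intentions of 0.24 or greater (corresponding to an effect size 0.16" on the SD scale. It assumes a design "in a design with 6 repeated measurements having a compound symmetry covariance structure", "when the standard deviation is 1.5", and that "the correlation between repeated observations on the same subject is 0.6 and the alpha level is 0.05". Against control, which has no repeated measures, it claims 0.27 (effect size 0.18). Tests are two-sided.

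No section gives a design effect, an effective sample size or a variance for the weights.

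**The concern.** The plan names two sampling design features that the model must handle: weights and repeated measures. The power statement models the second and is silent on the first. Combining a probability panel with an opt-in sample to match a national population will normally need unequal weights, and these reduce the information each participant contributes.

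What is at stake is the accuracy of the sensitivity claim. Someone reading the results would take 0.24 as the difference the primary comparison was able to detect with 80% power. If weighting costs precision, that figure belongs to an unweighted analysis that is not the one planned.

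**Working it through.** **Inputs.** From the Analytical Plan: n = 400 per arm, SD = 1.5, m = 6 measures, correlation 0.6, two-sided alpha 0.05, power 80%. The multiplier is 1.960 + 0.842 = 2.802. The weighting design effect (deff) is not in the documents; 1.2, 1.5 and 2.0 are assumed.

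**Reproducing the plan's figures, deff = 1.**
- Variance of a participant's mean of six measures: 1.5² × (1 + 5 × 0.6)/6 = 2.25 × 0.6667 = 1.50, so its SD is 1.2247.
- Text versus pictorial: 2.802 × √(2 × 1.50/400) = 2.802 × 0.0866 = 0.2426 (stated 0.24).
- Warning versus control (one measure, variance 2.25): 2.802 × √((1.50 + 2.25)/400) = 2.802 × 0.0968 = 0.2713 (stated 0.27).
- Effect sizes: 0.24/1.5 = 0.16 and 0.27/1.5 = 0.18, as stated.
- Power at exactly 0.24 is 79.1%, and at exactly 0.27 is 79.6%.

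Both figures therefore match to rounding with nothing left over for weighting.

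**Is there hidden slack?** The Design section allocates about 410 per arm, against 400 in the power statement. 410/400 = 1.025, so the extra ten per arm absorb a design effect of only about 1.025.

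**Adding a design effect.** Replace n by n/deff. Detectable differences scale by √deff, and power is Φ(difference/(SE × √deff) − 1.960). The last column takes intention as measured once per person: 2.802 × √(2 × 2.25/400) = 0.2972 before weighting.

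| deff | effective n per arm | text v pictorial | power at 0.24 | warning v control | power at 0.27 | one measure, any comparison |
|---|---|---|---|---|---|---|
| 1.0 | 400 | 0.243 | 79% | 0.271 | 80% | 0.297 |
| 1.2 | 333 | 0.266 | 72% | 0.297 | 72% | 0.326 |
| 1.5 | 267 | 0.297 | 62% | 0.332 | 62% | 0.364 |
| 2.0 | 200 | 0.343 | 50% | 0.384 | 50% | 0.420 |

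The last column matters because the Design section has participants answer the intention items after all the warnings have been viewed. That points to one measurement per person rather than six. It is a separate question from weighting, but both push the detectable difference upward, and correcting one leaves the other.

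**The case against.** Several points on the other side are fair.

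- **Nothing is miscalculated.** The stated figures follow from the stated inputs. The fault is an unstated assumption that deff = 1. This stands.
- **The size is assumed.** The documents say nothing about how variable the weights will be, so neither 1.2 nor 2.0 can be derived from them. At 1.2 the text-versus-pictorial figure moves only from 0.24 to 0.27. This stands too; only the direction is secure, and the n/deff approximation itself supposes weights largely unrelated to the outcome.
- **Other inputs could offset the loss.** The plan also fits a model adjusted for waterpipe use, other tobacco use and demographics. Since 1 − 1/deff is the R-squared needed, values of 0.17, 0.33 and 0.50 would offset design effects of 1.2, 1.5 and 2.0. Use status plausibly predicts intention, but the documents give no R-squared and the power statement claims no such gain. The SD of 1.5 may also be cautious for a mean of three 1-5 items: a true SD of 1.37 (1.5/√1.2) would offset 1.2, and 1.22 (1.5/√1.5) would offset 1.5. That remains a possibility only.
- **Model-based standard errors might not show the loss.** If the software's weighted standard errors ignored it, the price would appear instead as a type I error above 0.05: 2 × (1 − Φ(1.960/√deff)), or about 7% at deff 1.2 and 17% at 2.0. That does not rescue 80% power at alpha 0.05.

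A reader might infer more than this: that the weighted analysis cannot reach the stated power under any circumstances, that it can detect only clearly larger effects, or that a null result would be taken as excluding 0.24. The documents do not support these readings. The first two ignore the possible offset from adjustment and treat an assumed design effect as known. On the third, the plan reports detectability and does not say how a null result will be interpreted or call 0.24 a minimum important difference.

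**Conclusion.** The concern holds in limited form. The 0.24 and 0.27 are unweighted figures, while the primary model is to be weighted. With the other inputs fixed, and weights unequal and largely unrelated to the outcome, the unadjusted weighted comparison has less power than stated. For assumed design effects of 1.2 to 2.0, the detectable differences are about 0.27-0.34 for text versus pictorial and 0.30-0.38 for either warning arm versus control. Power at the stated differences is then 72-50% in both cases. If intention is measured once, the range is 0.33-0.42 for every comparison, from an unweighted 0.30.

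The direction rests on the plan's own text. The size rests wholly on the assumed range and would be trivial if the true design effect were close to 1. This is a correction to a stated figure; it does not show that the trial is too small or that the analysis is wrong.

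**What to change.** In the Analytical Plan:

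1. Restate the detectable differences and effect sizes with effective n = 400 divided by the design effect. Use the survey vendor's expected design effect for this blended sample, or tabulate 1.2, 1.5 and 2.0. The recent waterpipe survey mentioned under Interventions and Interactions is cited only for prevalence, and the documents do not say it was weighted or included opt-in respondents, so its design effect should not be carried over without checking.
2. Base the restated figures on the number of intention measurements actually taken per person, reconciling the six measures in the power statement with the Design section.
3. If a precision gain from covariate adjustment is to be claimed, state it separately with its assumed R-squared.

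The cost is a few lines of text and one figure from the vendor. Recruitment does not change; the stated detectable difference becomes less favourable. If the vendor expects a design effect near 1, one sentence saying so settles the weighting part of the point.

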Participants will be randomized to one of three conditions: text-only warnings, pictorial warnings, no warning control. Participants in the two intervention conditions will be shown six waterpipe packages, each with a different warning corresponding to their condition, in random order, and will complete items on package appeal and warning perceptions. Participants in the control condition will be shown one waterpipe package with no warning on it and will complete items on package appeal. The waterpipe package is a fictitious brand created by the study team in a separate study. All elements of the waterpipe packaging will be the same across conditions and the only difference will be the presence and type of warning.

Outcome Measure(s)

PRIMARY

Behavioral Intentions. The primary outcome is intention to smoke tobacco in a waterpipe within the next year, measured by averaging three items adapted from research on cigarette smoking:

1. How interested are you in smoking hookah in the next year?
2. How likely are you to smoke hookah in the next year?
3. How much do you plan to smoke hookah in the next year?

Response scale: (1) Not at all / (2) Very little / (3) Somewhat / (4) Quite a bit / (5) Very

SECONDARY

None

OTHER

Product Appeal. Three items will be used to measure how appealing each waterpipe tobacco package is to respondents, how likely they would be to try the product, and how much the packaging makes the respondent think that the product is harmful.

1. How appealing is this product to you?

2. How likely would you be to try this product?
3. How much does this packaging make you think this product is harmful?

Response scale: (1) Not at all / (2) A little / (3) Somewhat / (4) A lot

Mean Perceived Message Effectiveness (PME). This outcome will be measured using the 3-item Perceived Measured Effectiveness scale created by Noar and colleagues that includes items on attitudes, risk beliefs, and intentions. Overall scores are determined by summing the scores of the three items and dividing by three.

1. How much does this warning make smoking hookah seem unpleasant to you?
2. How much does this warning make you concerned about the health effects of smoking hookah?
3. How much does this warning discourage you from wanting to smoke hookah?

Response scale: (1) Not at all / (2) Very little / (3) Somewhat / (4) Quite a bit / (5) A great deal

Attention. One item to measure self-reported attention to the warning.

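### The power for the primary outcome assumes six intention scores per person, but intention is measured once: the detectable difference is about 0.30, not 0.24 or 0.27.

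*Combined protocol and SAP*

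**What the plan says.** **How intention is measured.** Under Outcome Measure(s), "The primary outcome is intention to smoke tobacco in a waterpipe within the next year, measured by averaging three items". The three items ask about interest, likelihood and plans over the next year; none refers to a particular warning or package. The Design section fixes the timing: "After viewing all warnings, participants will complete items on behavioral intentions, perceived risks of waterpipe smoking, and knowledge of risks".

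**What is repeated.** Under Interventions and Interactions, participants in the two warning conditions see six packages "in random order, and will complete items on package appeal and warning perceptions". Intention is not among the items answered at each package. Control participants see one package.

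**What the power statement assumes.** The Analytical Plan takes 400 people per condition and claims 80% power. For text versus pictorial it puts the detectable difference at 0.24 (effect size 0.16) and names intentions as the outcome. The calculation is set "in a design with 6 repeated measurements having a compound symmetry covariance structure", and its other inputs are SD 1.5, a within-person correlation of 0.6 and alpha 0.05. The remaining contrasts have their own sentence: "For comparisons between the text or pictorial warnings and the control condition (which does not have repeated measures), we will have 80% power". There the detectable difference is 0.27 (effect size 0.18). The same section describes the intention model as a PROC MIXED fit that accounts for sample weights and repeated measures.

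**The concern.** The power statement is attached by name to waterpipe intentions, and it singles out the control arm as the one without repeated measures. It therefore credits each warning-arm participant with six intention scores, when the measurement schedule yields one. Averaging six correlated scores reduces the variance of a person's mean; a single score has no such reduction.

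This is the only power statement for the only primary outcome; the plan lists no secondary outcomes. If the figures stand, readers will credit the trial with a 20% risk of missing a text-versus-pictorial difference of 0.24. On the plan's own SD that risk is about 38%, and a null result would be given more weight than the design supports.

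**Working it through.** **Inputs.** All are from the Analytical Plan unless noted: n = 400 per condition (the Design section plans about 410), SD = 1.5, correlation 0.6, six measurements, two-sided alpha 0.05, power 80%. The multiplier is z = 1.960 + 0.842 = 2.8016. The normal approximation is used throughout.

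**1. Reproduce the plan's figures.** The mean of six compound-symmetric measurements has variance SD² × (1 + 5 × 0.6)/6 = 0.667 × SD².

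- Text versus pictorial, six scores against six: 2.8016 × 1.5 × √(2 × 0.6667/400) = 0.243. The plan states 0.24.
- Warning versus control, six against one: 2.8016 × 1.5 × √((0.6667 + 1)/400) = 0.271. The plan states 0.27.

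Both figures match. The factor of 0.667 enters for both arms in the first and for the warning arm only in the second.

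**2. Use the measurement schedule in the protocol, one score per person in every arm.**

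- Standard error of the difference: 1.5 × √(2/400) = 0.10607.
- Detectable difference: 2.8016 × 0.10607 = 0.297, effect size 0.297/1.5 = 0.198. A t-based calculation gives 0.298. This applies to all three contrasts.
- With 410 per arm: 2.8016 × 1.5 × √(2/410) = 0.294.

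**3. Power at the stated differences.**

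- At 0.24: Φ(0.24/0.10607 − 1.960) = 62% (63% with 410 per arm).
- At 0.27: Φ(0.27/0.10607 − 1.960) = 72% (73% with 410 per arm).

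**4. Sample size for 80% power with one score.**

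- For 0.24: 2 × (2.8016 × 1.5/0.24)² = 613.2, so 614 per arm.
- For 0.27: 2 × (2.8016 × 1.5/0.27)² = 484.5, so 485 per arm.

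**5. Weighting.** The analysis will use survey weights, but the documents give no design effect. The values below are assumptions, shown only for scale. The detectable difference is 0.297 × √(design effect), and the standard error grows by the same factor.

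| Assumed design effect | Detectable difference | Power at 0.24 |
|---|---|---|
| 1.25 | 0.33 | 53% |
| 1.5 | 0.36 | 46% |
| 2.0 | 0.42 | 36% |

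**The case against.** The best defence is that actual power depends on quantities the plan leaves open, so the mismatch does not by itself prove the trial underpowered.

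- **SD.** The 1.5 comes from a cited study, and the plan does not say whether it describes this three-item average. It is large for a 1-to-5 scale, where the maximum is about 2. With one score and 400 per arm, an SD of 0.24/(2.8016 × √(2/400)) = 1.21 would give 80% power at 0.24, and 1.36 would give it at 0.27.
- **Covariates.** The plan also fits an adjusted model that includes waterpipe smoking status, and the sample mixes about 512 users with 718 susceptible non-users. An R² of 1 − (1.21/1.5)² ≈ 0.35 would restore 0.24.
- **Model wording.** With one row per participant, the mixed model reduces to ordinary linear regression, so the treatment estimate is unaffected. The arithmetic is also correct for the design it assumes.

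These points are fair as far as they go. A smaller SD or a useful R² could offset the loss, just as weighting could add to it. The plan, however, states neither a smaller SD nor any R²; it reaches its figures through six repeated measurements that the primary outcome does not have. Nor can the three intention items stand in for the repeats: they are averaged into one score, there are three rather than six, and control participants answer them too. The package item on likelihood of trying the product is repeated, but it belongs to Product Appeal, listed among the other outcomes. The model wording is the lesser part of the point.

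**Conclusion.** The concern holds. The stated detectable differences of 0.24 and 0.27 do not apply to an outcome measured once. Taking SD 1.5 as the SD of the single averaged score, with 400 per condition and two-sided alpha 0.05, 80% power corresponds to about 0.30 (effect size 0.20) for every pairwise contrast, unadjusted and unweighted. This is an inconsistency between the measurement schedule and the power statement, not a slip in calculation. The conclusion does not depend on the assumed design effects.

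**What to change.** In the Analytical Plan:

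1. Restate the primary power: 400 per condition gives 80% power for a difference in intentions of 0.30 (effect size 0.20) for each pairwise contrast, before weighting.
2. Obtain the expected design effect from NORC and multiply the detectable difference by its square root. If covariate adjustment is to be relied on for precision, state the assumed R² and its source.
3. Describe the intention model as having one row per participant, and remove the repeated-measures and compound-symmetry wording from it.
4. Keep the repeated-measures model, and any power based on six measurements, for outcomes rated per warning, such as perceived message effectiveness, emotional reactions and package appeal.

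The cost is wording and a less favourable headline figure. Recruitment, randomisation and data collection do not change.
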